## Clinical Investigational Plan

- Could not readily have been produced by the subject's clinical state or have been due to environmental or other interventions
- Follows a known pattern of response to intervention,
- Disappears or decreases with reduction in dose or cessation of intervention.

Additionally, AEs can be classified as *unrelated* if the causal relationship cannot be attributed to the device and/or procedure related.

Additional information may be requested, when required, by the Sponsor in order to support the reporting of AEs to regulatory authorities.

### 9.3 Anticipated AEs

Possible risks to the subjects include both device- and procedural-based risks. Below is a list of the potential adverse effects associated with the implant and use of the Axium Neurostimulator System.

Risks associated with any surgical procedure: abscess; cellulitis; excessive fibrotic tissue; wound dehiscence; wound, local or systemic infection; wound necrosis; edema; inflammation; foreign body reaction; hematoma; seroma; thrombosis; ischemia; embolism; thromboembolism; hemorrhage; thrombophlebitis; adverse reactions to anesthesia; hypertension; pulmonary complications; organ, nerve or muscular damage; gastrointestinal or genitourinary compromise; seizure, convulsion, or changes to mental status; complications of pregnancy including miscarriage and fetal birth defects; inability to resume activities of daily living; and death.

Risks associated with system placement procedures: pain at the implant site, swelling; infection, cerebrospinal fluid (CSF) leakage, CSF fistula, epidural hemorrhage, bacterial meningitis, seroma, weakness, hematoma, tissue damage, nerve damage, sensory loss, spinal cord compression; and paralysis. Patient use of anticoagulation therapies may increase the risk of procedure-related complications, such as hematomas, which could produce paralysis.

Risks associated with the use of the system: lead migration; INS migration; allergic response or tissue reaction to the implanted system material; hematoma or seroma at the implant site; skin erosion at the implant site; persistent pain at the INS and/or lead site, extension, or lead site; radicular chest wall stimulation; disturbed urination; dysesthesia; decubitus; headache; allodynia; hyperesthesia; premature battery depletion; loss of pain relief over time; escalating pain; clumsiness; numbness; temporary muscle activation; and uncomfortable stimulation or ineffective pain control caused by random failure of the system components or battery, changes in electrode position, loose electrical connections, lead or extension insulation breaches or fractures, lead retention, and inability to achieve the desired pain relief results.

An additional risk to the subject is pain due to setting the stimulation parameters too high as a result of the placement and stimulation of the lead in the area of the DRG.

Below is a list of the potential adverse effects associated with the implant and use of the DRG Neurostimulation System with Proclaim DRG IPG:

- Unpleasant sensations or motor disturbances, including involuntary movement, caused by stimulation at high outputs (if either occurs, turn off IPG immediately)

## Clinical Investigational Plan

- Undesirable changes in stimulation, which may be related to cellular changes in tissue around the electrodes, changes in electrode position
- Changes in stimulation or reduced pain relief due to loose electrical connections
- Changes in stimulation or reduced pain relief due to lead failure.
- Stimulation in unwanted places (such as stimulation of the chest wall)
- Lead migration, causing changes in stimulation or reduced pain relief
- Epidural hemorrhage
- Hematoma
- Infection
- Spinal cord compression
- Paralysis from placement of a lead in the epidural space
- Cerebrospinal fluid (CSF) leakage
- Tissue damage or nerve damage
- Paralysis, weakness, clumsiness, numbness, sensory loss below the level of the implant
- Pain below the level of the implant
- Pain or bleeding where the needle was inserted
- Persistent pain at the electrode or IPG site
- Escalating pain
- Seroma (mass or swelling) at the implant site
- Headache
- Allergic or rejection response to device or implant materials
- Implant migration
- Skin erosion around the implant
- Battery failure, leakage, or both
- Hardware malfunction that requires replacing the neurostimulator
- Pain from a noninjurious stimulus to the skin or an exaggerated sense of pain
- Formation of reactive tissue in the epidural space around the lead, which can cause delayed spinal cord compression and paralysis and requires surgical intervention (time to onset can range from weeks to many years after implant).

Additional risks to the patients, as a result of the placement and stimulation of the lead in the area of the dorsal root ganglion (DRG), include pain from setting the stimulation parameters too high. This may occur once the lead is in place and is connected to the neurostimulator and activated.

Below is a list of the potential adverse effects associated with the implant and use of MR Conditional Neurostimulation devices that may occur in the MRI environment:

- Lead electrode heating resulting in tissue damage or serious patient injury
- IPG heating resulting in tissue damage in the implant pocket or patient discomfort or both

## Clinical Investigational Plan

- Induced currents on leads resulting in overstimulation or shocking sensations
- Damage to the IPG or leads causing the system to fail to deliver stimulation or causing the system to deliver overstimulation
- Damage to the functionality or mechanical integrity of the IPG resulting in the inability to communicate with the IPG
- Movement or vibration of the IPG or leads

### 9.4 Subject Death

All patient deaths that occur during this investigation must be reported to St. Jude Medical as soon as possible (per Section 9.2). It is the investigator's responsibility to notify the IRB per the IRB policy. Should death occur, the investigator is required to record death information in the hospital records, and document the information on the case report form through the EDC system.

Subject Death may be an outcome of an SAE.

- Death is therefore related to an SAE: all efforts to obtain the SAE details should be made and the AE form must be completed or updated accordingly.
- The subject's death is an Early Conclusion of the subject's participation in the study. Therefore, the investigator is requested to complete the Withdrawal form.

### 9.5 Complaint Reporting

A complaint is defined as an inadequacy of a medical device with respect to its identity, quality, durability, reliability, safety or performance. Complaints may be submitted from the time of consent through the end of the study.

If a complaint involves an adverse device effect category or death as described in the protocol (Section 9.1-9.3), then the investigator shall notify the Sponsor by completing the adverse event or death case report form as applicable and must provide the Sponsor with all necessary documentation needed.

If the complaint does not involve a reportable adverse event per protocol, the investigator should notify the SJM Product Surveillance Department through one of the methods listed below as soon as possible after becoming aware of a complaint. The following is the contact information for reporting complaints: via email at [[contact]](mailto:[contact]) or by phone at [contact].

## 10.0 DATA ANALYSIS

The primary objective of this study is to demonstrate that the proportion of serious adverse effects (SAEs) at 12 months for subjects who receive a permanently implanted DRG stimulation system is lower than a pre-specified performance goal. The primary endpoint is the 12-month SAE rate from permanent implant until 12-month follow-up. [REDACTED]

## Clinical Investigational Plan

### 10.1 Primary Endpoint

The hypothesis is stated as follows:

$$H_0: p \geq 15.5\%$$

$$H_1: p < 15.5\%$$

where  $p$  is the 12-month SAE rate for subjects who receive the permanent Axium or Proclaim DRG IPG (proportion of subjects who experience at least one SAE from permanent implant through 12-month follow-up). The hypothesis will be tested at the 5% significance level. The analysis population will include subjects who received the permanent Axium or Proclaim DRG IPG, who either have an SAE after permanent implant or complete the 12-month follow-up visit.

The primary endpoint analysis will be conducted using Kaplan-Meier method on subjects who received the permanent Axium or Proclaim DRG IPG (primary analysis population). The serious adverse events (SAE) include adverse events which CEC adjudicates as serious events. The 12-month SAE rate will be estimated using Kaplan-Meier method with a 95% upper confidence bound (UCB) estimated using log-log transformation. If the 95% UCB is less than the 15.5%, the null hypothesis will be rejected.

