## Clinical Investigational Plan

inferiority between the DRG stimulation group compared to the SCS group with a pre-specified 10% non-inferiority margin. The study met the primary endpoint with statistically significantly more treatment successes in the DRG stimulation group compared to the SCS group at 3 months post permanent implant (81.2% vs. 55.7%, respectively;  $p = 0.0004$ ). This effect persisted at 12 months post implant (74.2% vs. 53.0%;  $p=0.0047$ ). Secondary and tertiary outcomes including percent change in VAS scores, change in SF-36 scores, change in Profile of Mood States (POMS) scores, and change in Brief Pain Inventory (BPI) scores were also suggestive of improvements in the group who received DRG stimulation compared to the SCS group.

The most commonly reported definitely-related adverse events (AEs) in the group who received DRG stimulation with the Axium Neurostimulator System in the ACCURATE IDE study were pain at the implantable pulse generator (IPG) pocket (14.5% of subjects) and loss of stimulation due to lead migration (11.8% of subjects). There were a total of 21 serious adverse events (SAEs) in 19 subjects reported in this study. The difference in overall rate of SAEs between the Axium and Control groups was not found to be statistically significantly different (Axium 10.5%, Control 14.5%,  $p=0.6248$ ). Additionally, the overall difference in the rate of SAEs during the system trial (Axium 1.3%, Control 3.9%,  $p=0.62$ ) and after the permanent implant (Axium 9.2%, Control 10.5%,  $p=1.0$ ) were not shown to be statistically significantly different. Only 1 serious adverse device effect (SADE; cardiac arrhythmia post-implant) was classified as possibly or definitely related to the device, procedure and/or stimulation in the group, which received the Axium Neurostimulator System. There were no reports of stimulation induced neurological deficits in either the control or Axium group at any point in the study.

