**Clinical Investigational Plan**

at up to 45 centers in the United States. A maximum of 426 subjects will be enrolled to achieve 319 subjects with a permanently implanted system, which will account for expected attrition, to yield 287 subjects for the primary analysis at 12 months post-implant (See Section 10.9 Sample Size for full details). After the last subject with a permanently implanted device reaches the 12-month study visit or crosses the 12-month study visit window, the endpoint analysis will be conducted and reported to the FDA.

After the subject signs the informed consent, s/he will be screened according to the inclusion/exclusion criteria and will undergo a baseline evaluation. Those subjects who meet the criteria for participation will undergo a trial of the DRG Neurostimulation System to assess response to DRG stimulation. Only subjects who report a 50% or greater reduction in overall pain intensity through direct patient-reported percentage of pain relief will receive the permanent implant. Device activation will occur according to the site's standard of care and may occur at the time of permanent system implant. Subjects will then return to the office for follow-up at 1, 3, 6 and 12 months post-permanent implant. Figure 2 below outlines subject flow through the study.

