### **8.11 Revisions, Replacements, or Explants (Additional Surgery)**

The subject and the implanting physician will collectively make the decision about any possible revision of the device based upon what is medically safe, what is desired by the subject, and what is in the subject's best medical interests. Any system revision, replacement or explant will be recorded on the appropriate eCRFs. If the device is explanted for any reason and re-implantation is not an option, the subject will be followed for 1 month post-explant and then withdrawn from the study. Subjects who undergo a revision or replacement procedure will resume their previous follow-up schedule.

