### 10.8 The Treatment of Missing, Unused, or Spurious Data, Including Drop-Outs and Withdrawals

Analyses of each endpoint will be performed in subjects who provide complete data for each endpoint. Subject accountability for enrolled subjects will be performed prior to analyses of the primary and secondary endpoints. There are no plans to perform imputations for missing data.

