### 10.9 The Exclusion of Particular Information for the Testing of the Hypothesis

There is no intent to exclude particular information for the testing of hypotheses.

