2.2.3 Survival Analyses

Survival analysis will be conducted to analyze the primary endpoint. Subjects without events will be censored at their last known event-free time point. Survival curves will be constructed using Kaplan-Meier estimates. The 95% confidence interval will be estimated using log-log transformation.

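### Protocol 10.1 gives two populations for the single primary test; one selects on the outcome and can miss the 15.5% goal that the all-implanted Kaplan-Meier analysis meets.

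*Protocol*

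**What the plan says.** Protocol 10.1 tests whether the 12-month SAE rate is below 15.5%. The test is at the 5% level, and the goal is met if the 95% upper confidence bound (log-log scale) is below 15.5%. Two statements of who is analysed follow each other:

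- The paragraph stating the hypothesis restricts the population to implanted subjects "who either have an SAE after permanent implant or complete the 12-month follow-up visit".
- The next paragraph runs the analysis "using Kaplan-Meier method on subjects who received the permanent Axium or Proclaim DRG IPG (primary analysis population").

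Other sections divide in the same way:

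- **Towards the restricted set.** Protocol 10.8: "Analyses of each endpoint will be performed in subjects who provide complete data for each endpoint". Protocol 5.0 plans 319 implanted subjects "to yield 287 subjects for the primary analysis at 12 months post-implant".
- **Towards all implanted.** Protocol 10.9: "There is no intent to exclude particular information for the testing of hypotheses". SAP 2.2.3: "Subjects without events will be censored at their last known event-free time point". SAP 2.3.1 repeats the all-implanted population of the second paragraph.

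SAP 2.1.1 (primary population), 2.9 (missing data) and 2.13 (sensitivity analysis) are redacted. The defect is therefore shown only in the protocol text.

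**The concern.** The study has one primary hypothesis and one decision rule, so it needs one population. Neither sentence in 10.1 is labelled as a sensitivity analysis, and nothing says which governs.

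The restricted rule is also unsound in itself. A subject who leaves at month 4 is kept if an SAE occurred before leaving and removed if not, so membership depends on the outcome. Event-free follow-up time leaves the denominator while every event stays in the numerator. Kaplan-Meier then has almost nothing to censor, which defeats the purpose of the censoring rule in SAP 2.2.3.

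At stake is the verdict on the 15.5% goal. In a band of event counts at the pass/fail boundary, the same data meet the goal under one sentence and miss it under the other. Choosing between them after the data are seen would be hard to defend.

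**Working it through.** **Inputs from the documents.** Goal 15.5%, 5% level, log-log upper bound (Protocol 10.1). 319 implanted and 287 for the primary analysis (Protocol 5.0), so 319 − 287 = 32 leavers, or 32/319 = 10.0%. Post-implant SAE rate in the device arm of the earlier trial: 9.2% (Protocol 2.0).

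**Assumptions.** No design SAE rate or power is visible, so true rates from 8% to 12% are examined. The bound is taken as one-sided 95%. SAE hazard is constant, dropout is non-informative and spread evenly over the year, and completers are observed to day 365.

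**Step 1: where 287 may come from.** In an exact binomial test with n = 287, H0 is rejected with at most 34 events. Type I error at 15.5% is 4.8%; power is 80.2% at 10.5% and 94.7% at 9.2%. 287 is the smallest n that reaches 80% power at 10.5%, and 287/0.90 = 318.9, which rounds up to 319. This suggests a design rate of 10.5%, but that is an inference.

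**Step 2: what the restricted rule computes.** With no one censored before 12 months, Kaplan-Meier reduces to

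rate = SAE subjects / (SAE subjects + event-free completers).

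With d events among n subjects and S = 1 − d/n, the upper bound is

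1 − exp{−L·exp(1.645·s/L)}, where L = −ln S and s = √[d/(n(n − d))].

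For d = 35, n = 287:

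- S = 252/287 = 0.8780 and L = 0.1300
- s = √[35/(287 × 252)] = 0.0220, so s/L = 0.169
- Bound = 1 − exp(−0.1300 × 1.321) = 15.8%

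**Step 3: the same data, all implanted.** The 32 leavers stay in the risk set until they leave. A rough check counts each as half a year: 35/(319 − 16) = 11.6%. The full Kaplan-Meier calculation, with events and leavers evenly spaced over 365 days, gives:

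| SAE subjects | Restricted: rate (bound) | All implanted: rate (bound) | Goal met? |
|---|---|---|---|
| 34 | 11.8% (15.4%) | 11.3% (14.7%) | both |
| 35 | 12.2% (15.8%) | 11.6% (15.0%) | all implanted only |
| 36 | 12.5% (16.2%) | 11.9% (15.4%) | all implanted only |
| 37 | 12.9% (16.6%) | 12.3% (15.8%) | neither |

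With 48 leavers the verdicts differ at 33 to 35 events, and with 64 at 30 to 33. With 16 leavers they differ only at 37. With 32 leavers and SAEs clustered in the first 60 days, they differ at 35 to 38.

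**Step 4: power** (simulation, 319 implanted, 10,000 runs per scenario).

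| True rate | Dropout | Restricted | All implanted |
|---|---|---|---|
| 8% | 10% | 98% | 99% |
| 9.2% | 10% | 90% | 95% |
| 10% | 10% | 79% | 88% |
| 10.5% | 10% | 70% | 81% |
| 12% | 10% | 38% | 52% |
| 9.2% | 5% | 94% | 95% |
| 10.5% | 5% | 77% | 82% |

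If half the SAEs fall in month 1, with 10% dropout, power is 88% against 96% at 9.2% and 66% against 82% at 10.5%.

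At a true 10.5% with 10% dropout, the mean estimate is 11.0% (restricted) against 10.5% (all implanted). At a true 15.5%, the test rejects in 2.0% against 4.5% of runs. With 10% dropout, the restricted set failed while the all-implanted set passed in 4.8% of runs at 9.2% and 11.5% at 10.5%. The reverse occurred in none of 110,000 runs.

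**The case against.** The visible text leans towards the sound analysis. Protocol 10.1 attaches the label of primary analysis population to all implanted subjects, SAP 2.3.1 repeats it, and the SAP 2.2.3 censoring rule makes little sense otherwise. The redacted SAP sections may settle the matter and may already contain a completer sensitivity analysis. This stands as a reason to expect the right analysis. It does not remove the contrary sentence from the protocol, which nothing subordinates to the SAP.

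Two of the supporting sections are weaker evidence than 10.1 itself. Protocol 10.9 is general and defines no population, and a censored follow-up time could be read as complete data under 10.8. Both points are fair; the contradiction within 10.1 does not depend on either section.

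The all-implanted estimate may also be biased. After an explant without re-implantation, "the subject will be followed for 1 month post-explant and then withdrawn from the study", so censoring may be informative. This stands: that the restricted rule overstates the true rate is conditional on non-informative dropout. That its estimate is never below the all-implanted one on the same data is not conditional.

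Finally, the larger power losses rest on assumed rates. At 9.2%, the only post-implant device-arm rate in the documents, the loss is about 5 points at 10% dropout and about 1 point at 5%. The calculations also assume completers are followed to day 365; those seen earlier would be censored under either rule.

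**Conclusion.** The concern holds. Protocol 10.1 names two populations for the only primary test, and the restricted one selects on the outcome. At the planned 319 implanted and 32 leavers, the choice decides the result at 35 or 36 SAE subjects when events are evenly spread. It costs about 5 points of power at a true 9.2% and about 11 at 10.5%, and shifts the estimate by about 0.5 points at 10.5%.

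The error is conservative: the cost is power and an ambiguous pre-specified test. The contradiction needs no assumption. Its size rests on assumed SAE rates, non-informative dropout and a one-sided bound. It should be fixed before the analysis.

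**What to change.** - In Protocol 10.1, delete the sentence restricting the population to subjects with an SAE or a completed 12-month visit. The primary analysis is then Kaplan-Meier at day 365 on all permanently implanted subjects, with event-free subjects censored at last event-free contact, as in SAP 2.2.3 and 2.3.1.
- In Protocol 10.8, exempt the primary endpoint from the complete-data rule.
- In Protocol 5.0, describe 287 as the number expected to reach 12 months.
- Confirm that the redacted SAP 2.1.1 and 2.9 agree.
- Unless the redacted SAP 2.13 already covers it, report the SAE-or-completer proportion as a conservative sensitivity analysis. Tabulate leavers by reason, with explant shown separately, so that informative censoring can be judged.

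The cost is protocol wording and a check of the redacted SAP sections. No new data are needed.

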### 10.2 Secondary Endpoints

#### 10.2.1 Reduction in pain intensity (VAS)

The endpoint will test whether subjects achieve a clinically relevant change (mean percentage reduction of at least 30%) in VAS score at 12 months from baseline. Percentage change in VAS score is calculated within each subject as:

$$\% \text{ Change in VAS score} = (\text{VAS at baseline} - \text{VAS at 12-month})/\text{VAS at baseline} * 100\%$$

The following hypothesis will be tested:

$$H_0: \text{Mean \% Change in VAS score} \leq 30\%$$

$$H_1: \text{Mean \% Change in VAS score} > 30\%$$

The hypothesis will be tested at the 5% significance level. The analysis will be carried out by calculating the 95% lower confidence bound (LCB) on the mean % Change in VAS from baseline to 12-month visit based on a t-distribution. If the 95% LCB is greater than 30.0%, the null hypothesis is rejected. The analysis population for this secondary endpoint will include subjects who complete both baseline and 12-month VAS scales, irrespective of IPG types.

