2.3.2 Secondary Endpoints

2.3.3 Reduction in pain intensity (VAS)

The endpoint will test whether subjects achieve a clinically relevant change (mean percentage reduction of at least [REDACTED]) in VAS score at 12 months from baseline.

Percentage change in VAS score is calculated within each subject as:

$$\% \text{ Change in VAS score} = (\text{VAS at baseline} - \text{VAS at 12-month})/\text{VAS at baseline} * 100\%$$

The following hypothesis will be tested:

[REDACTED]

The hypothesis will be tested at the 5% significance level. The analysis will be carried out by calculating the 95% lower confidence bound (LCB) on the mean % Change in VAS from baseline to 12-month visit based on a t-distribution. If the 95% LCB is greater than [REDACTED], the null hypothesis is rejected. The analysis population of this secondary endpoint will include primary analysis population subjects who complete both baseline and 12-month VAS scales.

Statistical Analysis Plan

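### The 30% VAS test covers 12-month completers only; a prespecified all-implanted analysis beside it would support a claim about everyone implanted (minor)

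*Protocol*

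**What the plan says.** Protocol 10.2.1 rejects the null hypothesis when the one-sided 95% lower confidence bound (t-distribution) of the mean percentage change exceeds 30%. Its population is stated openly: "The analysis population for this secondary endpoint will include subjects who complete both baseline and 12-month VAS scales, irrespective of IPG types". SAP 2.3.3 uses the same rule, with the threshold blacked out, in "primary analysis population subjects who complete both baseline and 12-month VAS scales".

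Protocol 10.8 adds: "There are no plans to perform imputations for missing data".

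Protocol 8.11 bears on who reaches month 12. Its rule for removed systems reads: "explanted for any reason and re-implantation is not an option, the subject will be followed for 1 month post-explant and then withdrawn". On the other hand, "Subjects who undergo a revision or replacement procedure will resume their previous follow-up schedule".

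Protocol 5.0 plans for 319 implanted subjects, "which will account for expected attrition, to yield 287 subjects for the primary analysis at 12 months post-implant".

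The plan also has measures that help to describe loss: a comparison of withdrawn with continuing subjects (Protocol 13.0), a summary of early-termination reasons (SAP 3.3), remote visits (Protocol 8.10), and VAS results at 1, 3 and 6 months (Protocol 4.5, SAP 3.5.1). None of these enters the 30% test. SAP 2.1.1, 2.7, 2.9, 2.13 and 4.1.1 are redacted.

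**The concern.** The endpoint is described as change to 12 months after permanent implant, and a reader may take a positive result as a statement about implanted subjects. The test says nothing about those without a 12-month VAS. In a randomised comparison, similar selective loss in both arms would partly cancel. Here one arm is compared with a fixed number, so any difference between completers and leavers passes straight into the estimate.

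There is a route by which leaving could follow poor relief. A subject explanted early enough and not re-implanted leaves before month 12, and Protocol 9.3 lists loss of pain relief and escalating pain among the anticipated effects. If leavers have less relief, the reported mean is too high for the implanted population and the error of a claim about that population exceeds 5%. The primary safety test is not affected. At stake are the size of the reported mean and the population for which it may be claimed.

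**Working it through.** **Inputs from the documents.** One-sided 5% test, threshold 30% (Protocol 10.2.1); 319 implanted, 287 at 12 months (Protocol 5.0).

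**Assumptions.** The documents give no SD of percentage change, so a range of 25 to 40 points is used. Loss of 12-month VAS is taken as 319 − 287 = 32, that is d = 32/319 = 0.1003. This is borrowed from the safety endpoint's planned flow. The true all-implanted mean is set at exactly 30%, the edge of the null hypothesis.

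**1. The plan's own figures.** If the completer mean is 30%, the test on n = 287 rejects in 5.0% of cases at every SD, so the stated level is reproduced for completers. The counts fit 10% loss: 287/0.90 = 318.9, rounded up to 319.

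**2. Error for a claim about all implanted subjects.** Let a share f of the 32 leavers have 0% change and the rest have the completer mean c. An all-implanted mean of 30% requires c = 30/(1 − d·f). The rejection probability is about 1 − Φ(1.645 − (c − 30)/(SD/√287)).

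Example with f = 0.5 and SD 30: c = 30/(1 − 0.0502) = 31.58; SE = 30/√287 = 1.771; shift = 1.58/1.771 = 0.89; rejection = 1 − Φ(0.75) = 23%.

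| Leavers | c | SD 25 | SD 30 | SD 35 | SD 40 |
|---|---|---|---|---|---|
| same as completers (f = 0) | 30.00 | 5% | 5% | 5% | 5% |
| a quarter at 0% | 30.77 | 13% | 11% | 10% | 9% |
| half at 0% | 31.58 | 28% | 23% | 19% | 16.5% |
| all at 0% (worst case) | 33.34 | 73% | 60% | 49% | 41% |
| leavers better (mean 40%) | 28.89 | 0.8% | 1.2% | 1.5% | 1.7% |

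With 16 of 319 missing (5%), the three selective-loss rows become 7–8%, 9.5–13% and 17–29%.

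**3. Where the decision can change.** As planned, the test passes when the completer mean exceeds 30 + 1.650·SD/√287. If all 32 leavers count as 0%, the pooled mean is m = 287c/319, and the pooled variance is [286·SD² + 287(c − m)² + 32m²]/318. Solving for a lower bound of 30 gives:

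| SD | Needed as planned | Needed with 32 zeros |
|---|---|---|
| 25 | 32.4% | 36.0% |
| 30 | 32.9% | 36.5% |
| 35 | 33.4% | 36.9% |
| 40 | 33.9% | 37.4% |

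Only a completer mean between the two columns gives a different answer. At a completer mean of 40% both analyses pass, and 51 to 60 of the 319 would have to be zeros for the test to fail. If 48 or 64 of 319 were missing and all counted as zero (15% or 20%), the second column would rise to about 38–40% or 41–42%.

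**4. Effect on the reported mean.** With a completer mean of 50% and all 32 leavers at 0%, the all-implanted mean is 50 × 287/319 = 45.0%. The decision stands but the figure is 5 points lower.

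**5. What imputation would gain.** This was simulated with 319 subjects, true mean 30%, SD 25 or 40, correlation between visits 0.5 or 0.7, and 10% missing at month 12. Log odds of leaving rose by 0.5 or 1.0 per SD less relief. When loss followed the 3- or 6-month score, the completer test rejected in 11–15% (0.5) or 19–30% (1.0) of runs, against 4–7% with multiple imputation. When loss followed the unseen 12-month score, the figures were 21–49% against 9–27%. A separate run at SD 30 agreed: 11–26% against 4–6% when loss followed the 6-month score, and 21–46% against 10–26% for the unseen score. These runs imputed normally distributed percentage change, without a baseline term or intermittent gaps, so they show direction and rough size only.

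**The case against.** The strongest reply is that the plan names its population and tests the mean in it at 5%. The excess error belongs to a wider claim that Protocol 10.2.1 does not state. This stands: a reader might infer that the test itself has an inflated type I error, and it does not.

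A reader might also infer that leavers are treatment failures. The documents do not show that. Explant is for any reason, revised or replaced subjects stay in follow-up, a missed visit does not end participation, and neither an explant rate nor a breakdown of expected attrition is given. If leavers did better, the error would be below 5%. The 41–73% figure needs every leaver at 0% and is a bound, not an expectation.

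Nor can it be said that the plan lacks a sensitivity analysis. The redacted SAP sections include those headed missing data, sensitivity analysis and imputation, and may contain one.

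Finally, it is tempting to place the likely mean by the earlier trial's 12-month success rate of 74.2% (Protocol 2.0). That figure is a composite: at least 50% relief in both the trial phase and follow-up, with no stimulation-induced neurological deficit. It does not give a 12-month responder rate among implanted subjects, so it neither settles nor sharpens the point. The pre-implant gate in Protocol 5.0 ("Only subjects who report a 50% or greater reduction in overall pain intensity through direct patient-reported percentage of pain relief") makes a mean well above 30% plausible, but it concerns relief in a short trial phase, not at 12 months.

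What remains is that the visible rule answers a narrower question than a reader is likely to ask, and that interim scores which could help to answer the wider one are already collected.

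**Conclusion.** The concern holds as a minor point. The completer test is valid for completers. It overstates relief in all implanted subjects if leavers do worse, a direction that is plausible but not demonstrated. Under the stated assumptions, the error of the wider claim at the 30% boundary is 9–13% with a quarter of leavers at 0% and 16–28% with half.

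The decision is sensitive only if the completer mean falls at roughly 32–37%. That band rests on 10% loss. VAS loss could be larger, because the 287 is a safety-endpoint count: Protocol 10.1 includes a subject with an SAE even without a 12-month visit. Protocol 8.10 also allows a numeric rating scale in place of the VAS at remote visits without saying whether that completes the VAS. Above the band, only the size of the reported mean is affected.

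**What to change.** Keep the prespecified completer test. In Protocol 10.2.1 and 10.8 and SAP 2.3.3, unless the redacted SAP sections already do so:

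- Add a prespecified analysis of the mean percentage change in all permanently implanted subjects with a baseline VAS, using multiple imputation of the 12-month VAS from baseline and the 1-, 3- and 6-month VAS. State how deaths are treated.
- Add one sensitivity analysis that counts scores missing after explant or for lack of effect as 0% change. It is needed because imputation reduces, but does not remove, bias that depends on the unseen score.
- Claim relief above 30% for implanted subjects only if the all-implanted lower bound also exceeds 30%. Otherwise word the conclusion as applying to 12-month completers.

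Cost: wording for one secondary endpoint, a little programming, and any agreement needed to add an analysis in a study that is a condition of approval. No new data are required. The all-implanted mean may be less favourable than the completer mean.
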